8.0 Dose Delay Criteria Based on Adverse Events

For events with an attribution of possibly, probably or definitely related to study medication, strictly follow the modifications in this table for the first **two** cycles, until individual treatment tolerance can be ascertained. Thereafter, these modifications should be regarded as guidelines. If multiple adverse events are seen, administer dose based on greatest reduction required for any single adverse event observed. Reductions or increases apply to treatment given in the preceding cycle and are based on adverse events observed since the prior dose.

ALERT: ***ADR reporting may be required for some adverse events (See Section 10)***

8.1 No dose reductions or escalations are allowed for nivolumab.

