Gastrointestinal disorders	Pancreatitis	Nivolumab	
Grade 2: Hold nivolumab until resolution, maximum 3 weeks.
 
If >3 weeks, discontinue nivolumab and patient goes to event monitoring.
 
Grade 3 or Grade 4, hold nivolumab until Grade 2 or better then reintroduce
 
If it recurs, the drug is discontinued and patient goes to event monitoring
 
Any \geqGrade 3 drug-related amylase or lipase abnormality that is not associated with symptoms or clinical manifestations of pancreatitis does not require dose delay
 
The PI should be consulted for \geqGrade 3 amylase or lipase abnormalities

Gastrointestinal disorders	Diarrhea	Nivolumab	
Grade ≥ 2 despite maximal supportive care: Hold drug until resolution to baseline grade. If suspicious and clinically indicated, initiate work up to rule out infectious causes and colitis
 
Grade 3 or 4 despite maximal supportive care: Discontinue drug and start corticosteroids until resolution to baseline and patient goes to event monitoring. If suspicious and clinically indicated, initiate work up to rule out infectious causes and colitis

	Colitis	Nivolumab	
Grade ≥ 2: Hold drug until resolution to baseline grade
 
Grade ≥ 3: Discontinue drug and start

CTCAE System/Organ/Class (SOC)	Event	Agent	Action
			corticosteroids until resolution to baseline grade and patient goes to event monitoring
General disorders and administration site conditions	Fatigue	Nivolumab	Grade 3: Hold drug until Grade 2 or better
Metabolism and nutrition disorders	Hyperglycemia	Nivolumab	Grade 4: Permanently discontinue nivolumab
Respiratory, thoracic and mediastinal disorders	Pneumonitis	Nivolumab	Grade ≥ 2 : Hold drug and start corticosteroids until resolution to baseline grade Grade ≥ 3 : Discontinue nivolumab and initiate treatment with high doses of corticosteroids and patient goes to event monitoring
	Cough	Nivolumab	Grade ≥ 2 : Hold drug and start corticosteroids until resolution to baseline grade Grade ≥ 3 : Discontinue nivolumab and initiate treatment with high doses of corticosteroids and patient goes to event monitoring
	Dyspnea	Nivolumab	Grade ≥ 2 : Hold drug until resolution to baseline grade
All other hematologic and non-hematologic	All other hematologic and non-hematologic	Nivolumab	Grade ≥ 2 : Hold nivolumab until resolution to Grade 1 or baseline, except for lymphopenia and leukopenia NOTE: Grade 3 lymphopenia or leukopenia do not require dose delay

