8.3 Discontinuation Criteria for Nivolumab

Treatment should be permanently discontinued for the following:

- Any Grade 2 drug-related uveitis or eye pain or blurred vision that does not respond to topical therapy and does not improve to Grade 1 severity within the re-treatment period OR requires systemic treatment
- Any Grade 3 non-skin, drug-related adverse event lasting >7 days, with the following exceptions for drug-related laboratory abnormalities, uveitis, pneumonitis, bronchospasm, hypersensitivity reactions, and infusion reactions, and endocrinopathies:
 - Grade 3 drug-related uveitis, pneumonitis, bronchospasm, hypersensitivity reaction, or infusion reaction of any duration requires discontinuation
 - Grade 3 drug-related endocrinopathies adequately controlled with only physiologic hormone replacement do not require discontinuation
 - Grade 3 drug-related laboratory abnormalities do not require treatment discontinuation except those noted below

- Grade 3 drug-related thrombocytopenia >7 days or associated with bleeding requires discontinuation
- Any drug-related liver function test (LFT) abnormality that meets the following criteria require discontinuation:
 - AST or ALT >8 x ULN
 - Total bilirubin >5 x ULN
 - Concurrent AST or ALT >3 x ULN and total bilirubin >2 x ULN
- Any Grade 4 drug-related adverse event or laboratory abnormality, except for the following events which do not require discontinuation:
 - Isolated Grade 4 amylase or lipase abnormalities that are not associated with symptoms or clinical manifestations of pancreatitis and decrease to < Grade 4 within 1 week of onset.
 - Isolated Grade 4 electrolyte imbalances/abnormalities that are not associated with clinical sequelae and are corrected with supplementation/appropriate management within 72 hours of their onset
 - Grade 4 lymphopenia or leucopenia
 - Grade 4 drug-related endocrinopathy adverse events, such as adrenal insufficiency, ACTH deficiency, hyper- or hypothyroidism, or glucose intolerance, which resolve or are adequately controlled with physiologic hormone replacement (corticosteroids, thyroid hormones) or glucose-controlling agents, respectively, may not require discontinuation after discussion with and approval from the Investigator [as allowed by protocol]
- Any dosing interruption lasting >6 weeks with the following exceptions:

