 - Dosing delays or interruptions to allow for prolonged steroid tapers to manage drug-related adverse events are allowed. Prior to re-initiating treatment in a subject with a dosing interruption lasting >6 weeks, the Investigator must be consulted. Tumor assessments should continue as per protocol even if dosing is interrupted or delayed
 - Dosing interruptions or delays lasting >6 weeks that occur for non-drug-related reasons may be allowed if approved by the Investigator. Prior to re-initiating treatment in a subject with a dosing interruption lasting >6 weeks, the Investigator must be consulted. Tumor assessments should continue as per protocol even if dosing is interrupted
- Any adverse event, laboratory abnormality, or intercurrent illness which, in the judgment of the Investigator, presents a substantial clinical risk to the subject with continued nivolumab dosing

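### The catch-all hold in Section 8.2 and the 6-week rule in Section 8.3 can undo Section 8.3's own exceptions for endocrinopathy controlled on hormone replacement

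*Combined protocol and SAP*

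**What the plan says.** The Section 8.2 table gives dose-delay actions by event. Its only endocrine or metabolic row is hyperglycemia: "Grade 4: Permanently discontinue nivolumab". Every event without its own row goes to the last row, All other, which at Grade 2 or higher says: "Hold nivolumab until resolution to Grade 1 or baseline, except for lymphopenia and leukopenia".

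Section 8.3 lists grounds for permanent discontinuation. Three of them matter here.

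- Grade 3 non-skin events lasting more than 7 days are a ground, but: "Grade 3 drug-related endocrinopathies adequately controlled with only physiologic hormone replacement do not require discontinuation".
- Grade 4 events are a ground, but endocrinopathies (glucose intolerance is among the examples) that resolve or are adequately controlled "may not require discontinuation after discussion with and approval from the Investigator".
- A separate ground is "Any dosing interruption lasting >6 weeks with the following exceptions". The two exceptions are "Dosing delays or interruptions to allow for prolonged steroid tapers to manage drug-related adverse events are allowed" and "Dosing interruptions or delays lasting >6 weeks that occur for non-drug-related reasons may be allowed if approved by the Investigator".

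Section 8.0 sets how binding the table is. It is to be followed strictly for the first two "cycles, until individual treatment tolerance can be ascertained. Thereafter, these modifications should be regarded as guidelines". Section 8.2 also refers to the management algorithms in Appendix II, one of which is for endocrinopathy.

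**The concern.** Section 8.3 treats a controlled endocrinopathy as something that need not cost the patient the drug. The catch-all row ends a hold only when the grade falls to 1 or returns to baseline, and it takes no account of control. A patient well controlled on replacement, but still graded 2 or higher, could be held until the 6-week limit passes and then be discontinued under a different bullet of the same Section 8.3.

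The primary endpoint is response within 12 cycles (Section 2.1), and Section 16.311 counts CR or PR as the objective status during therapy. Patients who leave treatment for reasons other than progression move to event monitoring (Section 13.3). Lost treatment can therefore affect exposure within the response window, treatment length in responders and the tally of discontinuations for toxicity. The final decision separates 5 from 6 successes in 35 patients (Section 16.2), so even a few patients handled differently are worth avoiding.

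**Working it through.** There is no power or error-rate figure to reproduce. The check sets the rules side by side, with some schedule arithmetic.

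**Step 1: which row applies.** No row in Section 8.2 names thyroid, adrenal or pituitary events. A drug-related event of this kind at Grade 2 or higher therefore falls to All other. The named exemptions there are lymphopenia and leukopenia only.

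**Step 2: how long a controlled event may keep its grade.** The Grade 3 endocrinopathy bullet is an exception to a trigger for events lasting more than 7 days. It has work to do only if a controlled event can still be Grade 3 after 7 days. The Grade 4 bullet separates events that resolve from events that are adequately controlled. The protocol thus expects control without resolution, but the text supports this to 7 days and not to 6 × 7 = 42 days. The CTCAE grade definitions are not reproduced. Persistence beyond 42 days is an assumption.

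**Step 3: whether a 6-week exception applies.** The first needs a steroid taper, so it covers an endocrinopathy managed that way but not one on stable replacement alone. The second needs a non-drug-related reason, which a drug-related endocrinopathy is not. With cycles of 14 days, 42 / 14 = 3 dosing intervals pass before the limit; with 28-day cycles, 42 / 28 = 1.5.

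**Step 4: when the hold is mandatory.** The table is strict for 2 × 14 = 28 days, or longer in calendar time if a hold stops the cycle count. Because 28 is less than 42, a discontinuation that is mandatory throughout requires both an event in the first two cycles and a cycle count that stops during the hold. The first scheduled on-treatment thyroid test is at the end of Cycle 4, day 4 × 14 = 56 (±7 days), or at the third month under the footnote to Section 4.1. Thyroid events found by scheduled tests therefore arise after the strict period. Events found through symptoms could come earlier.

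**Step 5: how many patients.** Section 15.17 lists hypothyroidism at 1% to 10%. In 35 evaluable patients that is 35 × 0.01 = 0.35 to 35 × 0.10 = 3.5. Adrenal insufficiency, hypophysitis and thyroiditis are listed at 0.1% to <1%, which is below 35 × 0.01 = 0.35 patients each. These frequencies are not restricted by grade. The conflict also needs the event to be drug-related, Grade 2 or higher, above baseline for more than 42 days despite control, and without a steroid taper. No rate for that combination is given, so the hypothyroidism figure is a ceiling and not an estimate.

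**Step 6: signs of an omission.** Two other Section 8.3 exceptions have counterparts in Section 8.2: lymphopenia/leukopenia, and amylase or lipase abnormalities without pancreatitis. Controlled endocrinopathy has none.

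**Step 7: a companion conflict.** For Grade 4 hyperglycemia, Section 8.2 says "Grade 4: Permanently discontinue nivolumab". For Grade 4 glucose intolerance controlled with glucose-controlling agents, Section 8.3 says "may not require discontinuation after discussion with and approval from the Investigator". The terms differ, but where both describe the same event the actions differ at once. Neither persistence nor the 6-week clock is needed.

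**The case against.** A reader might infer that the catch-all row always ends treatment in patients whom Section 8.3 expressly allows to continue. The documents do not support that, for these reasons, all of which stand.

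- After two cycles the Section 8.2 table is a guideline. An investigator may keep dosing a controlled patient, and then the 6-week clock never starts.
- The Section 8.3 bullets lift the Grade 3 and Grade 4 triggers. They do not say that dosing continues without a hold, and they do not lift the 6-week trigger. The Grade 4 bullet is conditional on approval. Holding first, and not discontinuing on grade alone, is a coherent sequence.
- If control brings the event to Grade 1 or baseline, dosing resumes and nothing conflicts. Patients who enter on thyroid replacement, as Section 3.24 permits, need only return to baseline.
- Cases on a prolonged steroid taper are already excepted.
- The flowchart of the Appendix II endocrinopathy algorithm is not visible in the text available for this check, and it may address dosing on replacement. Its absence there is not a fault of the plan.

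It would also be wrong to infer that up to 3.5 patients are expected to lose treatment, since that is the any-grade ceiling from Section 15.17.

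These points narrow the concern without removing it. The guideline sentence softens the Section 8.2 table but not the Section 8.3 list, so a site that follows the recommended hold still meets the 6-week criterion. Whatever Appendix II shows, the catch-all row and the 6-week rule would still have to agree with it.

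**Conclusion.** The conflict is real but narrow. Read literally, the catch-all row and the 6-week rule together can defeat the purpose of the Section 8.3 exceptions for controlled endocrinopathy. This rests on the assumption that the controlled event stays at Grade 2 or higher and above baseline for more than 6 weeks with no steroid taper under way.

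The hold is mandatory only in the first two cycles. After that the likely consequence is that one site holds under Section 8.2 while another doses in reliance on Section 8.3, rather than a forced discontinuation. The number of patients is unknown and at most a few of 35, and no effect on the response rate can be quantified from the documents. The Grade 4 glucose conflict is more direct and needs no persistence assumption. The point merits correction because the rules disagree as written and the correction is cheap.

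**What to change.** In one protocol amendment:

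- Reconcile the All other row of Section 8.2, the rule on interruptions of more than 6 weeks, the Section 8.3 endocrinopathy exceptions and the Appendix II endocrinopathy algorithm, so that all lead to the same action for a patient controlled on hormone replacement. A separate endocrinopathy row or a clause in the All other row would do for Section 8.2. State explicitly how the 6-week rule applies to these patients.
- Reconcile the Section 8.2 hyperglycemia row with the Section 8.3 bullet on controlled Grade 4 glucose intolerance.

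The sponsor chooses the clinical rule in both cases; this review takes no view on which is right. The cost is about one table row and one or two clauses, with no added visits, tests or patients and no change to the statistical design.

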8.3 Discontinuation Criteria for Nivolumab

Treatment should be permanently discontinued for the following:

- Any Grade 2 drug-related uveitis or eye pain or blurred vision that does not respond to topical therapy and does not improve to Grade 1 severity within the re-treatment period OR requires systemic treatment
- Any Grade 3 non-skin, drug-related adverse event lasting >7 days, with the following exceptions for drug-related laboratory abnormalities, uveitis, pneumonitis, bronchospasm, hypersensitivity reactions, and infusion reactions, and endocrinopathies:
 - Grade 3 drug-related uveitis, pneumonitis, bronchospasm, hypersensitivity reaction, or infusion reaction of any duration requires discontinuation
 - Grade 3 drug-related endocrinopathies adequately controlled with only physiologic hormone replacement do not require discontinuation
 - Grade 3 drug-related laboratory abnormalities do not require treatment discontinuation except those noted below

- Grade 3 drug-related thrombocytopenia >7 days or associated with bleeding requires discontinuation
- Any drug-related liver function test (LFT) abnormality that meets the following criteria require discontinuation:
 - AST or ALT >8 x ULN
 - Total bilirubin >5 x ULN
 - Concurrent AST or ALT >3 x ULN and total bilirubin >2 x ULN
- Any Grade 4 drug-related adverse event or laboratory abnormality, except for the following events which do not require discontinuation:
 - Isolated Grade 4 amylase or lipase abnormalities that are not associated with symptoms or clinical manifestations of pancreatitis and decrease to < Grade 4 within 1 week of onset.
 - Isolated Grade 4 electrolyte imbalances/abnormalities that are not associated with clinical sequelae and are corrected with supplementation/appropriate management within 72 hours of their onset
 - Grade 4 lymphopenia or leucopenia
 - Grade 4 drug-related endocrinopathy adverse events, such as adrenal insufficiency, ACTH deficiency, hyper- or hypothyroidism, or glucose intolerance, which resolve or are adequately controlled with physiologic hormone replacement (corticosteroids, thyroid hormones) or glucose-controlling agents, respectively, may not require discontinuation after discussion with and approval from the Investigator [as allowed by protocol]
- Any dosing interruption lasting >6 weeks with the following exceptions:
 - Dosing delays or interruptions to allow for prolonged steroid tapers to manage drug-related adverse events are allowed. Prior to re-initiating treatment in a subject with a dosing interruption lasting >6 weeks, the Investigator must be consulted. Tumor assessments should continue as per protocol even if dosing is interrupted or delayed
 - Dosing interruptions or delays lasting >6 weeks that occur for non-drug-related reasons may be allowed if approved by the Investigator. Prior to re-initiating treatment in a subject with a dosing interruption lasting >6 weeks, the Investigator must be consulted. Tumor assessments should continue as per protocol even if dosing is interrupted
- Any adverse event, laboratory abnormality, or intercurrent illness which, in the judgment of the Investigator, presents a substantial clinical risk to the subject with continued nivolumab dosing

9.0 Ancillary Treatment/Supportive Care

9.1 Full supportive care

Patients should receive full supportive care while on this study. This includes blood product support, antibiotic treatment, and treatment of other newly diagnosed or concurrent medical conditions. All blood products and concomitant medications such as antidiarrheals, analgesics, and/or antiemetics received from the first day of study treatment administration until 30 days after the final dose will be recorded in the medical records.

9.2 Blood products and growth factors

Blood products and growth factors should be utilized as clinically warranted and following institutional policies and recommendations. The use of growth factors should follow published guidelines of the Journal of Clinical Oncology, Volume 33, No 28 (October 1), 2015: pp. 3199-3212 (WBC growth factors) AND Journal of Clinical Oncology, Volume 28, No 33 (November 20), 2010: pp. 4955-5010 (darbepoetin/epoetin).

9.3 Antiemetics

Antiemetics may be used at the discretion of the attending physician.

9.4 Diarrhea

Diarrhea can be managed conservatively with loperamide. The recommended dose of loperamide is 4 mg at first onset, followed by 2 mg every 2-4 hours until diarrhea free (maximum 16 mg/day).

In the event of Grade 3 or 4 diarrhea, the following supportive measures are allowed: hydration, octreotide, and antidiarrheals.

If diarrhea is severe (requiring intravenous rehydration) and/or associated with fever or severe neutropenia (Grade 3 or 4), broad-spectrum antibiotics must be prescribed. Patients with severe diarrhea or any diarrhea associated with severe nausea or vomiting **should be hospitalized** for intravenous hydration and correction of electrolyte imbalances.

If suspicious and clinically indicated, initiate work up to rule out infectious causes and colitis at treating physician's discretion.

9.5 Hepatotoxicity

As there is potential for hepatic toxicity with nivolumab, drugs with a predisposition to hepatotoxicity should be used with caution in patients treated with nivolumab-containing regimen.

9.6 Additional adverse events

Please refer to [Appendix II](#) for additional Adverse Event Management Algorithms excerpted from the investigator's brochure for nivolumab (version 15).

10.0 Adverse Event (AE) Reporting and Monitoring

The site principal investigator is responsible for reporting any/all serious adverse events to the sponsor as described within the protocol, regardless of attribution to study agent or treatment procedure.

The sponsor/sponsor-investigator is responsible for notifying FDA and all participating investigators in a written safety report of any of the following:

- Any suspected adverse reaction that is both serious and unexpected.
- Any findings from laboratory animal or *in vitro* testing that suggest a significant risk for human subjects, including reports of mutagenicity, teratogenicity, or carcinogenicity.
- Any findings from epidemiological studies, pooled analysis of multiple studies, or clinical studies, whether or not conducted under an IND and whether or not conducted by the sponsor, that suggest a significant risk in humans exposed to the drug
- Any clinically important increase in the rate of a serious suspected adverse reaction over the rate stated in the protocol or Investigator’s Brochure (IB).

Summary of SAE Reporting for this study
(please read entire section for specific instructions):

WHO:	WHAT form:	WHERE to send:
All sites	Pregnancy Reporting http://ctep.cancer.gov/protocolDevelopment/electronic_applications/docs/PregnancyReportFormUpdated.pdf	Global Pharmacovigilance & Epidemiology Bristol-Myers Squibb Company Fax Number: [REDACTED] Email: [REDACTED] Mayo Sites – attach to MCCC Electronic SAE Reporting Form
Mayo Clinic Sites	Mayo Clinic Cancer Center SAE Reporting Form http://livecycle2.mayo.edu/workspace/?startEndpoint=MC4158-56/Processes/MC4158-56-Process.MC4158-56 AND attach MedWatch 3500A: http://www.fda.gov/downloads/AboutFDA/ReportsManualsForms/Forms/UCM048334.pdf	Global Pharmacovigilance & Epidemiology Bristol-Myers Squibb Company Fax Number: [REDACTED] Email: [REDACTED] Will automatically be sent to [contact]

Definitions

Adverse Event

Any untoward medical occurrence associated with the use of a drug in humans, whether or not considered drug related.

Suspected Adverse Reaction

Any adverse event for which there is a reasonable possibility that the drug caused the adverse event.

Expedited Reporting

Events reported to sponsor within 24 hours, 5 days or 10 days of study team becoming aware of the event.

Routine Reporting

Events reported to sponsor via case report forms

Events of Interest

Events that would not typically be considered to meet the criteria for expedited reporting, but that for a specific protocol are being reported via expedited means in order to facilitate the review of safety data (may be requested by the FDA or the sponsor).

